#### Clinical Practice Research Datalink GOLD (CPRD GOLD), United Kingdom (University of Oxford)

The Clinical Practice Research Datalink (CPRD) is a governmental, not-for-profit research service, jointly funded by the National Institute for Health and Care Research and the Medicines and Healthcare products Regulatory Agency, a part of the Department of Health, United Kingdom (UK) (<https://cprd.com>). CPRD GOLD(20) comprises computerized records of all clinical and referral events in primary care in addition to comprehensive demographic information and medication prescription data in a sample of UK patients (predominantly from Scotland (52% of practices) and Wales (28% of practices). The prescription records include information on the type of product, date of prescription, strength, dosage, quantity, and route of administration. Data from contributing practices are collected and processed into research databases. Quality checks on patient and practice level are applied during the initial processing. Data are available for 20 million patients, including 3.2 million currently registered patients.

Access to CPRD GOLD data requires approval via the Research Data Governance Process. CPRD GOLD will be onboarded as Data Partner for DARWIN EU® in 2023.

#### IQVIA Disease Analyser (DA) Germany, Germany

DA Germany is collected from extracts of patient management software used by GPs and specialists practicing in ambulatory care settings. (21) Data coverage includes more than 34M distinct person records out of a total population of 80M (42.5%) in the country and collected from 2,734 providers. Patient visiting more than one provider are not cross identified for data protection reasons and therefore recorded as separate in the system. Dates of service include from 1992 through present. Observation time is defined by the first and last consultation dates. Germany has no mandatory GP system and patient have free choice of specialist. As a result, data are collected from visits to 28.8% General, 13.4% Orthopaedic Surgery, 11.8% Otolaryngology, 11.2% Dermatology, 7.7% Obstetrics/Gynaecology, 6.2% various Neurology and Psychiatry 7.0% Paediatric, 4.6% Urology, 3.7% Cardiology, 3.5% Gastroenterology, 1.5% Pulmonary and 0.7% Rheumatology practices. Drugs are recorded as prescriptions of marketed products. No registration or approval is required for drug utilisation studies.

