#### Integrated Primary Care Information Project (IPCI), The Netherlands

	D2.2.3 –Study Protocol for P2 C1-008	
	Author(s): [name], [name]	Version: v3.1 – Final
		Dissemination level: public

IPCI is collected from electronic health records (EHR) of patients registered with their general practitioners (GPs) throughout the Netherlands. (23) The selection of 374 GP practices is representative of the entire country. The database contains records from 2.8 million patients out of a Dutch population of 17M starting in 1996. (23) The median follow-up is 4.7 years. The observation period for a patient is determined by the date of registration at the GP and the date of leave/death. The observation period start date is refined by many quality indicators, e.g., exclusion of peaks of conditions when registering at the GP. All data before the observation period is kept as history data. Drugs are captured as prescription records with product, quantity, dosing directions, strength and indication. Drugs not prescribed in the GP setting might be underreported. Indications are available as diagnoses by the GPs and, indirectly, from secondary care providers but the latter might not be complete. Approval needs to be obtained for each study from the Governance Board. (23)

Information System for Research in Primary Care (SIDIAP), Spain

SIDIAP is collected from EHR records of patients receiving primary care delivered through Primary Care Teams, consisting of GPs, nurses and non-clinical staff. (24) The Catalan Health Institute manages 328 out of 370 such Primary Care Teams with a coverage of 5.8M patients, out of 7.8M people in the Catalan population (74%). The database started to collect data in 2006. The mean follow-up is 15 years. The observation period for a patient can be the start of the database (2006), or when a person is assigned to a Catalan Health Institute primary care centre. Date of exit can be when a person is transferred-out to a primary care centre that does not pertain to the Catalan Health Institute, or date of death, or date of end of follow-up in the database. Drug information is available from prescriptions and from dispensing records in pharmacies. Drugs not prescribed in the GP setting might be underreported; and disease diagnoses made at specialist care settings are not included. Studies using SIDIAP data require previous approval by both a Scientific and an Ethics Committee.

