### 8.4 Follow-up

Patient-level characterisation: study participants will be followed from the date of MDD diagnosis (index date) until the earliest of loss to follow-up, end of data availability, death, or end of study period (31st December 2022). Additionally:

- To assess the proportions of patients with newly diagnosed MDD initiating antidepressant therapy, incident MDD cases will be followed from the date of MDD diagnosis (index date) until the first prescription of the antidepressant class of interest, up to 24 weeks following MDD diagnosis.
- To assess the proportions of patients with newly diagnosed MDD switching or discontinuing specific antidepressant therapy, incident MDD cases on antidepressant therapy will be followed from the date of the first prescription of the specific antidepressant class of interest up to the date of specific intervals (4, 6, 8, 12, and 24 weeks) after starting antidepressant therapy.
- To assess the proportions of patients with newly diagnosed MDD starting, switching and discontinuing concomitant therapy with psycholeptics, incident MDD cases on antidepressant therapy will be followed from the date of the first prescription of the specific antidepressant class of interest up to the date of specific intervals (4, 6, 8, 12, and 24 weeks) after starting antidepressant therapy.

Patient-level utilization of antidepressants: study participants will be followed up from the date of incident prescription and/or dispensation of antidepressant class of interest (index date) until the earliest of loss to follow-up, end of data availability, death, or end of study period (31st December 2022).

	D2.2.3 –Study Protocol for P2 C1-008	
	Author(s): [name], [name]	Version: v3.0 – Revised
	Dissemination level: Confidential	

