#### Patient-level characterisation: Treatment initiation, switching, and discontinuation

To characterise treatment of MDD, the number and percentages of patients receiving each of a pre-specified list of MDD treatments (as listed in section 8.6.1) will be described at index date, and 4, 6, 8, 12, and 24 weeks post index date. The criteria for treatment switching and discontinuation will be based on the options currently available in the standard analytical tools that will be used in this project, specifically, the “TreatmentPattern” R package. This analysis will produce sunburst plots and Sankey diagrams to describe treatment initiation, switching and discontinuation over time (objectives 1 and 3).

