For the treatment pattern analysis, we will look at specific time intervals following treatment initiation namely at week 4, 6, 8, 12 and 24 following treatment initiation. Only patients with sufficient follow-up at these intervals will be included for this analysis, implying that patients for instance which were initially included for the analysis at week 4 might not longer be included at week 6 because of lost to follow-up. As part of the results, we will provide the number of individuals included in the analysis at the different time intervals which will provide information on the extent of people who dropped out from the analysis. If the percentage of people who dropped from the analysis at week 24 is high (where high is defined as more than 50% of individuals participating at week 4 do not longer participate at week 24), we will do a sensitivity analysis where i) we assume that the people who were lost for follow-up continued treatment and ii) we assume that the people who were lost to follow-up discontinued treatment. As this analysis can not be generated by the treatment pattern package, we will only do this for the overall analysis (thus not stratified by age and sex).

The number of pills (per package) of the antidepressant of interest might vary by countries which might bias the proportion of individuals continuing treatment. Indeed, if the antidepressant is dosed as one pill daily, and the initial prescription is a package of 30 pills, by definition the patient will be considered as having continued treatment at week 4 even if the patient discontinued treatment in the meantime. To contextualize this potential misclassification, we will provide information on the median quantity (with min, max, P25 and P75) by type of antidepressant and by database.

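### In IQVIA DA Germany, patients who stop treatment and never return leave the discontinuation denominator instead of being counted, and the planned sensitivity analysis may not show it

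*Protocol*

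**What the plan says.** - **Observation in DA Germany (section 8.2).** "Observation time is defined by the first and last consultation dates". The same paragraph adds that "Patient visiting more than one provider are not cross identified for data protection reasons", so a patient who moves to another practice becomes a new record.
- **Follow-up (section 8.4).** One rule serves every database: patients are followed "until the earliest of loss to follow-up, end of data availability, death, or end of study period".
- **Denominator (section 11).** For weeks 4, 6, 8, 12 and 24 after initiation, "Only patients with sufficient follow-up at these intervals will be included for this analysis". The number analysed at each timepoint will be reported.
- **Discontinuation (section 8.8.3).** "The criteria for treatment switching and discontinuation will be based on the options currently available in the standard analytical tools". The parameter table sets a 7-day collapse window but gives no rule for a patient whose observation ends before the supply does.
- **Contrast (section 8.2).** For IPCI, "The observation period for a patient is determined by the date of registration at the GP and the date of leave/death". SIDIAP ends at transfer out, death or end of follow-up. The protocol does not say how observation ends in CPRD GOLD or IMASIS.
- **Safeguard (sections 8.8.4 and 11).** If more than 50% of those analysed at week 4 are no longer analysed at week 24, two scenarios are run, one counting lost patients as continuing and one as discontinued. They are run overall only, not by age or sex.

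**The concern.** In DA Germany the event that keeps a patient under observation is a consultation, and a consultation is normally also what produces the next prescription. Leaving observation is therefore tied to the outcome. If a patient stops and the prescribing visit turns out to be the last visit to that practice, there is no follow-up after it, and the complete-case rule removes the patient from every later timepoint.

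Replacing the complete-case rule with censoring at the end of observation would not solve this, because the censoring would be informative.

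The study is meant to show whether intercurrent events occur in practice as often as in trials, and results are shown database by database. Readers will set the German discontinuation figures beside the Dutch and Catalan ones. Section 11 discusses loss to follow-up in general but does not link it to the German observation rule or warn about that comparison.

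**Working it through.** The protocol states no expected discontinuation or loss rate, so there is no figure to reproduce. All rates below are assumptions.

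**Notation.** D is true discontinuation by a given week. u is the share of stoppers no longer observed at that week. m is the share of continuers no longer observed, for example after an unlinked change of practice.

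**1. Complete-case estimate (section 11 denominator)**

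E = D(1−u) / [D(1−u) + (1−D)(1−m)]

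E < D is equivalent to (1−D)(1−u) < (1−D)(1−m), that is, u > m. The direction depends only on whether stoppers are lost more often than continuers.

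**2. Size, with D = 50%**

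| Stoppers still observed (1−u) | m = 0 | m = 10% | m = 20% |
|---|---|---|---|
| 90% | 0.45/0.95 = 47.4% | 0.45/0.90 = 50.0% | 0.45/0.85 = 52.9% |
| 75% | 0.375/0.875 = 42.9% | 0.375/0.825 = 45.5% | 0.375/0.775 = 48.4% |
| 50% | 0.25/0.75 = 33.3% | 0.25/0.70 = 35.7% | 0.25/0.65 = 38.5% |
| 25% | 0.125/0.625 = 20.0% | 0.125/0.575 = 21.7% | 0.125/0.525 = 23.8% |

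For other values of D, with u = 50% and m = 0: D = 30% gives 0.15/0.85 = 17.6% (−12.4 points), and D = 70% gives 0.35/0.65 = 53.8% (−16.2 points).

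**3. Does the sensitivity analysis catch it?**

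Let x be the share of initiators lost before week 4 and y the share lost between weeks 4 and 24. The trigger needs y/(1−x) > 0.50.

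- With x = 30% and y = 30%, 60% of initiators are lost by week 24, but the trigger reads 0.30/0.70 = 42.9% and does not fire.
- With x = 30%, y must exceed 35%, so more than 65% of all initiators must be lost before anything is run.
- In the same example, suppose all lost patients stopped and 30% of those still observed stopped. The truth is 0.60 + 0.30 × 0.40 = 72%. The complete-case estimate is 30%. The lost-equals-discontinued scenario, if it used the week-4 base, would give (0.30 + 0.12)/0.70 = 60%.

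Patients whose prescribing visit is their last never enter the week-4 base, so the trigger cannot register them.

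**4. The same two scenarios on all initiators**

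Counting the lost as continuing gives D(1−u). Counting them as discontinued gives D + (1−D)m. With D = 50%, u = 50% and m = 10%, these are 25% and 55%. They contain the true 50%, while the complete-case figure is 35.7%.

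**The case against.** **The look-back limits the problem.** Patients need at least 365 days of data before entry. In DA Germany that means a consultation at the same practice at least a year earlier, so single-contact patients are already excluded. To be missing at week 24, an established patient must have no later consultation there, for any reason, up to the end of the data. This stands, and it is why the 90% row belongs in the table. It narrows the affected group without removing it, and the documents give no return rate.

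**The direction is not certain.** Continuers who change provider are lost as well, since "Patient visiting more than one provider are not cross identified for data protection reasons and therefore recorded as separate in the system". This also stands. With u = 0 and m = 10%, the estimate at D = 50% is 0.50/0.95 = 52.6%, above the truth. That u exceeds m is plausible, because continuing at a practice normally requires going back, but it is a judgement and not a documented fact.

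**The protocol already handles loss.** Section 11 discloses the shrinking denominator, promises the counts and specifies both extreme scenarios. Credit is due: the remedy is largely there. What is missing is certainty that it runs, a base that includes early losses, and any mention of the German rule.

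**Software behaviour is unseen.** How the package treats supply extending past the end of observation is not stated. The point does not depend on it, because the exclusion in section 11 operates on follow-up.

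**Conclusion.** The concern holds in this form: in DA Germany, loss from the discontinuation analysis depends on the outcome, and the planned safeguard does not reliably expose it. Discontinuation is understated if stoppers are lost more often than continuers. With all continuers observed and true discontinuation of 50%, the understatement runs from about 3 points (90% of stoppers still observed) to 30 points (25%). Where in that range the study falls cannot be taken from the documents. Comparison with IPCI and SIDIAP is affected because their observation ends on administrative dates.

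A reader might infer more, but the documents do not support it:

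- **Initiation overstated.** The follow-up restriction in section 11 is stated for intervals after treatment initiation. Table 9 applies initiation to all incident MDD patients, so short follow-up does not clearly remove anyone.
- **Duration under Objective 2 lost.** Section 8.8.3 takes duration from recorded exposure start and end dates. Truncation at the end of observation is not stated.
- **A large share of the study affected.** Table 4 counts active subjects across all specialties, not MDD initiators, and databases are not pooled.
- **The last-consultation estimate as a lower bound.** It can exceed the truth when continuers are lost more often, as the 52.6% example shows.

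**What to change.** In section 8.8.4, for IQVIA DA Germany:

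- Run the lost-equals-continued and lost-equals-discontinued scenarios unconditionally, with all antidepressant initiators as the base at every timepoint.
- Date discontinuation at the end of supply plus the 7-day gap already used for collapsing eras, so that lost patients still covered at an early timepoint are not counted as stopped there.
- Report both results as bounds beside the complete-case estimate.
- Label the outcome as discontinuation at the recorded practice.

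In section 11, state that observation in DA Germany ends at the last consultation, that this can depend on stopping treatment, and that it limits comparison with databases whose observation ends on registration-type dates.

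The cost is a few sentences of protocol text and a small additional analysis in one database, outside the standard package. The scenarios can stay overall only, as now planned. The main drawback is that the lost-equals-discontinued bound counts patients who changed practice as stopping, which is why both bounds and the label are needed.

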#### Institut Municipal Assistència Sanitària Information System (IMASIS), Spain

The Institut Municipal Assistència Sanitària Information System (IMASIS) is the Electronic Health Record (EHR) system of Parc de Salut Mar Barcelona (PSMar) which is a complete healthcare services organisation. (22) Currently, this information system includes and shares the clinical information of two general hospitals (Hospital del Mar and Hospital de l'Esperança), one mental health care centre (Centre [name]) and one social-healthcare centre (Centre Fòrum) including emergency room settings, which are offering specific and different services in the Barcelona city area (Spain). At present, IMASIS includes clinical information more than 1 million patients with at least one diagnosis and who have used the services of this healthcare system since 1990 and from different settings such as admissions, outpatients, emergency room and major ambulatory surgery. The diagnoses are coded using The International Classification of Diseases ICD-9-CM and ICD-10-CM. The average follow-up period per patient in years is 6.37 (SD±6.82). IMASIS-2 is the anonymized relational database of IMASIS which is used for mapping to OMOP including additional sources of information such as the Tumours Registry.

#### Integrated Primary Care Information Project (IPCI), The Netherlands

	D2.2.3 –Study Protocol for P2 C1-008	
	Author(s): [name], [name]	Version: v3.1 – Final
		Dissemination level: public

IPCI is collected from electronic health records (EHR) of patients registered with their general practitioners (GPs) throughout the Netherlands. (23) The selection of 374 GP practices is representative of the entire country. The database contains records from 2.8 million patients out of a Dutch population of 17M starting in 1996. (23) The median follow-up is 4.7 years. The observation period for a patient is determined by the date of registration at the GP and the date of leave/death. The observation period start date is refined by many quality indicators, e.g., exclusion of peaks of conditions when registering at the GP. All data before the observation period is kept as history data. Drugs are captured as prescription records with product, quantity, dosing directions, strength and indication. Drugs not prescribed in the GP setting might be underreported. Indications are available as diagnoses by the GPs and, indirectly, from secondary care providers but the latter might not be complete. Approval needs to be obtained for each study from the Governance Board. (23)

Information System for Research in Primary Care (SIDIAP), Spain

SIDIAP is collected from EHR records of patients receiving primary care delivered through Primary Care Teams, consisting of GPs, nurses and non-clinical staff. (24) The Catalan Health Institute manages 328 out of 370 such Primary Care Teams with a coverage of 5.8M patients, out of 7.8M people in the Catalan population (74%). The database started to collect data in 2006. The mean follow-up is 15 years. The observation period for a patient can be the start of the database (2006), or when a person is assigned to a Catalan Health Institute primary care centre. Date of exit can be when a person is transferred-out to a primary care centre that does not pertain to the Catalan Health Institute, or date of death, or date of end of follow-up in the database. Drug information is available from prescriptions and from dispensing records in pharmacies. Drugs not prescribed in the GP setting might be underreported; and disease diagnoses made at specialist care settings are not included. Studies using SIDIAP data require previous approval by both a Scientific and an Ethics Committee.

	D2.2.3 –Study Protocol for P2 C1-008	
	Author(s): [name], [name]	Version: v3.0 – Revised
		Dissemination level: Confidential

### 8.3 Study Period

The study period will be from 1st of January 2013 to 31st December 2022 or the end of available data in each of the data sources if earlier (see Table 4 for more details).

### 8.4 Follow-up

Patient-level characterisation: study participants will be followed from the date of MDD diagnosis (index date) until the earliest of loss to follow-up, end of data availability, death, or end of study period (31st December 2022). Additionally:

- To assess the proportions of patients with newly diagnosed MDD initiating antidepressant therapy, incident MDD cases will be followed from the date of MDD diagnosis (index date) until the first prescription of the antidepressant class of interest, up to 24 weeks following MDD diagnosis.
- To assess the proportions of patients with newly diagnosed MDD switching or discontinuing specific antidepressant therapy, incident MDD cases on antidepressant therapy will be followed from the date of the first prescription of the specific antidepressant class of interest up to the date of specific intervals (4, 6, 8, 12, and 24 weeks) after starting antidepressant therapy.
- To assess the proportions of patients with newly diagnosed MDD starting, switching and discontinuing concomitant therapy with psycholeptics, incident MDD cases on antidepressant therapy will be followed from the date of the first prescription of the specific antidepressant class of interest up to the date of specific intervals (4, 6, 8, 12, and 24 weeks) after starting antidepressant therapy.

Patient-level utilization of antidepressants: study participants will be followed up from the date of incident prescription and/or dispensation of antidepressant class of interest (index date) until the earliest of loss to follow-up, end of data availability, death, or end of study period (31st December 2022).

	D2.2.3 –Study Protocol for P2 C1-008	
	Author(s): [name], [name]	Version: v3.0 – Revised
	Dissemination level: Confidential	

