### Data analyses

Objective 1: The number and percentage of patients with newly diagnosed MDD initiating treatment with antidepressants will be estimated at 4, 6, 8, 12, and 24 weeks after date of new MDD diagnosis; and the number and percentage of those discontinuing and switching treatment at 4, 6, 8, 12, and 24 weeks following start of antidepressant therapy. They will be reported in tabular form as absolute numbers as well as

	D2.2.3 –Study Protocol for P2 C1-008	
	Author(s): [name], [name]	Version: v3.1 – Final
		Dissemination level: public

proportions, and depicted using Sunburst plots and Sankey diagrams. The statistical analyses will be performed based on OMOP-CDM mapped data using the “TreatmentPatterns” R package.

Objective 2: The duration (mean, median, quantiles 25% and 75%, minimum and maximum) of antidepressant use in patients with newly diagnosed MDD during the first treatment era will be estimated. The index date will be determined as the date of the first prescription of the specific antidepressant class for each individual. Statistical analyses will be conducted using the "DrugUtilization" R package based on OMOP-CDM mapped data.

Objective 3: The number and percentage of patients with newly diagnosed MDD initiating, switching, or discontinuing treatment with psycholeptics) will be estimated at 4, 6, 8, 12, and 24 weeks after the date of treatment initiation with antidepressants; and at 4, 6, 8, 12, and 24 weeks after starting psycholeptics (for switching or discontinuing treatment). This will be reported in tabular form as absolute numbers as well as proportions and depicted using Sunburst plots and Sankey diagrams. The statistical analyses will be performed based on OMOP-CDM mapped data using the “TreatmentPatterns” R package.

For all analyses, results will be reported with a minimum cell count of 5, and any counts smaller than 5 will be reported as <5 to ensure privacy and confidentiality.

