## 8.5 Study Population with inclusion and exclusion criteria

### 8.5.1 Patient-level characterization of MDD treatment

The study cohort will comprise all patients, aged  $\geq 12$  years, with newly diagnosed MDD present in the respective databases during the study period (2013-2022) and with at least 365 days of data availability before the day they become eligible for study inclusion.

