**Table 9. Operational Definitions of Outcome**

Outcome name	Details	Primary outcome?	Type of outcome?	Wahout window	Care Setting	Code Type	Diagnosis Position	Applied to study populations	Measurement characteristics/validation	Source of algorithm
Treatment initiation	Preliminary code lists provided in Table 7	Yes	Binary: Counts and percentages	365 days as incident use only	IP and OP care	RxNorm	N/A	All patients with incident MDD	N/A	N/A
Treatment Switching	Preliminary code lists provided in Table 7	Yes	Binary: Counts and percentages	365 days as incident use only	IP and OP care	RxNorm	N/A	All patients with incident MDD undergoing treatment	N/A	N/A
Treatment Discontinuation	Preliminary code lists provided in Table 7	Yes	Binary: Counts and percentages	365 days as incident use only	IP and OP care	RxNorm	N/A	All patients with incident MDD undergoing treatment	N/A	N/A

IP = inpatient, OP = outpatient, n/a = not applicable

	D2.2.3 –Study Protocol for P2 C1-008	
	Author(s): [name], [name]	Version: v3.0 – Revised
		Dissemination level: Confidential

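### The short-follow-up rule runs only from treatment start, so initiation at 4 to 24 weeks after diagnosis has no stated denominator rule and, read literally, is modestly understated

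*Protocol*

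**What the plan says.** Initiation is the first half of Objective 1 and is measured from diagnosis. The abstract (Data analyses, Objective 1) says that the number and percentage "initiating treatment with antidepressants will be estimated at 4, 6, 8, 12, and 24 weeks after date of new MDD diagnosis". Section 8.4, first bullet, follows incident cases "until the first prescription of the antidepressant class of interest, up to 24 weeks following MDD diagnosis". The same section ends follow-up at loss, end of data, death or 31 December 2022, whichever comes first.

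Table 9 gives the outcome type for initiation as "Binary: Counts and percentages" and the population as "All patients with incident MDD". Entry under 8.5.1 looks backward only: patients qualify "with at least 365 days of data availability before the day they become eligible for study inclusion". Nothing is required after diagnosis.

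Two places deal with incomplete follow-up. Section 11 includes at each time point only patients followed long enough, and introduces this with "we will look at specific time intervals following treatment initiation". Section 8.8.4, triggered when more than half of the week-4 participants are gone by week 24, scores lost patients first as having continued treatment and then as having discontinued it. The ENCePP checklist (item 10.7) points to 8.8.4 as the place where missing data are handled.

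**The concern.** A patient diagnosed in autumn 2022, or one who leaves the database a few weeks after diagnosis, may still be untreated when observation ends. Whether that patient would have started by week 24 is unknown. The section 11 rule counts weeks from treatment start, and an untreated patient has no such date. Continuing and discontinuing, the two scenarios in 8.8.4, have no meaning for someone not on treatment. So neither provision, as worded, reaches the initiation proportion.

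What remains is a crude percentage over all incident cases. The numerator can then only lose later initiators, while the denominator keeps everyone. The shortfall grows from week 4 to week 24 because more patients are cut off as the window lengthens. Results are shown by database, so databases with more early loss would be affected more.

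**Working it through.** The protocol states no expected initiation proportion and no loss rate, so there is no figure of its own to reproduce. The roughly 380,000 patients in 8.7 are a feasibility count.

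**Inputs from the protocol.** Study period 1 January 2013 to 31 December 2022 = 3,652 days (8.3). Window 24 weeks = 168 days (8.4). Denominator: all incident MDD patients (Table 9).

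**Assumptions, not in the protocol.** Diagnoses uniform over the study period. True week-24 initiation p = 30% to 70%. A share f = 0 to 80% of those initiators start on the day of diagnosis, the rest evenly over the 168 days. Loss by week 24 L = 0 to 50%, at a constant rate. Censoring independent of initiation.

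**Step 1: share of diagnoses too close to the study end.** Days in window divided by 3,652:

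- week 4: 28/3,652 = 0.8%
- week 12: 84/3,652 = 2.3%
- week 24: 168/3,652 = 4.6%

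For IPCI, with data lock on 01/12/2022, week 24 gives 168/3,622 = 4.6% as well.

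**Step 2: effect of the study end alone.** A patient who would start on day t is still observed then with probability 1 − t/3,652. Averaged over 0 to 168 days this is 1 − 84/3,652 = 0.977. Only later starters are affected, so

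understatement = p × (1 − f) × 84/3,652 = p × (1 − f) × 0.0230.

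- p = 0.7, f = 0: 0.7 × 0.0230 = 1.6 points
- p = 0.5, f = 0.5: 0.25 × 0.0230 = 0.6 points
- p = 0.3, f = 0.8: 0.06 × 0.0230 = 0.1 points

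**Step 3: adding loss to follow-up.** The probability of still being observed at day t becomes G(t) = (1 − t/3,652) × exp(−λt), with λ = −ln(1 − L)/168. The crude proportion is p × f + p × (1 − f) × mean G. The share with under 24 weeks of observation is 1 − G(168).

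**Step 4: three possible denominators, true p = 50%, f from 0 to 0.8.**

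| Assumed loss by week 24 | Share under 24 weeks | All incident patients | Sufficient follow-up from diagnosis, everyone | Only censored non-initiators dropped |
|---|---|---|---|---|
| none (study end only) | 4.6% | 48.8–49.8% | 50.0% | 50.6–51.1% |
| 10% | 14.1% | 46.4–49.3% | 50.0% | 51.9–53.4% |
| 25% | 28.5% | 42.5–48.5% | 50.0% | 54.3–57.5% |
| 50% | 52.3% | 35.3–47.1% | 50.0% | 59.7–66.4% |

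The last column is c/[c + (1 − p) × G(168)], where c is the crude proportion. Early initiators are kept whatever their later observation, while non-initiators must complete 24 weeks, so the proportion is too high.

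Over p = 30% to 70%, the understatement with all incident patients in the denominator is 0.1–1.6 points from the study end alone, 0.4–5.1 with 10% loss, 0.9–10.5 with 25% and 1.8–20.5 with 50%.

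**The case against.** The strongest reply is that section 11 can be read more widely. It introduces its rule for the treatment pattern analysis as a whole. Section 10 lists initiation among treatment patterns, and 8.8.3 treats initiation, switching and discontinuation together at weeks counted from an index date, which 8.4 sets at diagnosis. On that reading, patients with short follow-up are excluded and the understatement disappears. This is a fair reading of intent, but the rule's own wording ties its intervals to treatment start, so the text does not settle the matter.

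A reader might infer that Table 9 itself scores short-follow-up patients as non-initiators. It does not. It names a population and an outcome type, and its rows for switching and discontinuation have the same form although section 11 restricts those analyses. Nor are all patients with short follow-up at issue: one who starts before observation ends is counted correctly. A reader might also infer that the bias must be downward. That holds only for the literal denominator; the table under the working shows no bias or upward bias under the other two.

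It is also tempting to turn the follow-up figures in 8.2 into exit rates per database. They describe whole databases, not patients after an MDD diagnosis, and they already contain end-of-data censoring, which would then be counted twice. SIDIAP shows the problem: with data from 2006 to the end of 2022, about 17 years, an exit rate of 1/15 per year would give a mean of 15 × (1 − exp(−17/15)) = 10.2 years, not the stated 15. Dividing the 380,000 equally over five databases to obtain standard errors is equally unsupported, since Table 4 lists 0.6 to 8.5 million active subjects. The protocol therefore does not show that differences between countries would be artefacts.

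Finally, denominator detail often belongs in an analysis plan. Here, though, the protocol itself fixes the population, the clock and a short-follow-up rule, and words that rule for a clock this outcome does not use.

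**Conclusion.** The point stands as a mismatch between two clocks. Initiation is counted from diagnosis in all incident patients, while the only provisions for short follow-up count from treatment start. Followed literally, the plan understates initiation. From the study end alone the effect is modest: about 0.1 to 1.6 points at week 24, assuming uniform entry, 30% to 70% true initiation, up to 80% of initiators starting on the day of diagnosis, and independent censoring.

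The effect is larger where early loss is high. The protocol does not give that loss. IQVIA DA Germany deserves attention because 8.2 defines its observation time by first and last consultation, so a patient who does not return is censored at once; how often this happens cannot be derived from the document. The direction depends on the denominator finally programmed, which is the reason to state it.

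**What to change.** In 8.8.3 and section 11, state that for initiation the sufficient-follow-up rule runs from diagnosis: at each of weeks 4, 6, 8, 12 and 24, include only patients with at least that many weeks between diagnosis and end of observation, initiators and non-initiators alike. Report the number excluded at each week, by database.

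For the overall, unstratified analysis, add a cumulative incidence of initiation from diagnosis, censored at end of observation and with death as a competing event. This matches the limit that 8.8.4 already sets on work outside the package.

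The cost is a sentence or two, a little code outside the package, and some patients at each time point: on the uniform-entry assumption 0.8% at week 4 and 4.6% at week 24 from the study end, plus those lost early. Both estimates still rely on censoring being unrelated to treatment. Where observation ends at the last consultation that may not hold, since treated patients may return more often, so the report should say so for IQVIA DA Germany.
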